### **Sites within the United States**

#### **No exemestane starter supplies will be available for this study.**

Once a patient has been randomized, patient specific supplies will be sent automatically to the registering investigator and should arrive within 10 days. Exemestane requests are transmitted by the ECOG-ACRIN Operations Office – Boston the day the patient is randomized and will be processed by PMB the next business day and shipped the following business day. Shipments within the United States are sent by FedEx ground (generally three to five day delivery). Thus, if a patient is registered on Monday, ECOG-

ACRIN would enter a clinical drug request for that patient on Monday and PMB would process that request on Tuesday and ship the drug on Wednesday. United States sites could expect to receive their order approximately Wednesday. Shipments to United States sites can be expedited (i.e., receipt on Thursday in example above) by the provision of an express courier account name and number to the ECOG-ACRIN Operations Office – Boston at the time the patient is randomized.

The initial request will be for 3 bottles of Exemestane. Ten (10) weeks after the initial electronic request [i.e., two (2) weeks before needed], sites may reorder an additional 3 bottles of Exemestane by using the PMB Online Agent Order Processing (OAOP) application (<https://eapps-ctep.nci.nih.gov/OAOP/pages/login.jsp>). Access to OAOP requires the establishment of a CTEP Identity and Access Management (IAM) account (<https://eapps-ctep.nci.nih.gov/iam/>) and the maintenance of an “active” account status and a “current” password. The assigned patient ID number (e.g., "999999") and the patient initials (e.g., "L,FM") must be entered in the "Patient or Special Code" field. A separate order is required for each patient ID number (e.g., "999999") being ordered. All drug orders will be shipped directly to the physician responsible for treating the patient.

Each open label, patient-specific bottle will be labeled with:

- The protocol number (i.e., “E2112”)
- The bottle number (i.e., “Bottle 1 of 3, 2 of 3, 3 of 3”)
- The number of tablets (i.e., “30 tablets”)
- The patient ID number (e.g., "44444", where “44444” represents a unique patient identifier assigned at randomization)
- The patient initials (i.e., first initial, last initial [e.g., "FL"])
- The agent identification (i.e., “Exemestane 25 mg”)
- A blank line for the pharmacist to enter the patient’s name
- Administration instructions
- Storage instructions (i.e., Store at 25°C (77°F), excursions permitted from 15°C to 30° C (59-86 °F) )
- Emergency contact instructions
- A Julian date

The Julian date indicates the day the bottles were labeled and shipped and is composed of the last two digits of the calendar year (e.g., 2016 = 16, 2017 = 17) and a day count (e.g., January 1 = 001, December 31 = 365). For example, a bottle labeled and shipped on January 1, 2016 would have a Julian date of ‘16001’ and a bottle labeled and shipped on December 31, 2016 would have a Julian date of ‘16365’. The Julian date will be used by PMB for recalls. When a lot expires, PMB will determine the last date the expired lot was shipped and will recall all bottles shipped on or before that date.

**Special Ordering Procedures for Patients Requiring a Dose Reduction:** If the patient is **dose reduced** from entinostat/placebo **5 mg** once a week TO entinostat/placebo **3 mg** once a week (see Section [5.4.1](#)), a request must be placed by using the PMB Online Agent Order Processing (OAOP) application to obtain the entinostat 1 mg and matched placebo tablets.

**Drug Transfers:** Patient specific study drug supplies MAY NOT be transferred from one patient to another patient or from one protocol to another protocol. All other transfers (e.g., a patient moves from one participating clinical site to another participating clinical

site, the principal investigator at a given clinical site changes) must be approved in advance by the PMB. To obtain an approval for transfer, investigators should complete and submit to the PMB ([contact]) a Transfer Investigational Agent Form available on the CTEP home page (<http://ctep.cancer.gov>) or by calling the PMB at [contact]. The patient ID number (e.g., "44444") and the patient initials (e.g., "FL") should be entered in the "Received on NCI Protocol No." and the "Transferred to NCI Protocol No." fields in addition to the protocol number (i.e., "E2112").

**Drug Returns: Only undispensed clinical supplies should be returned to the PMB.**

When it is necessary to return study drug investigators should return the study drug to the PMB using the NCI Return Drug List available on the CTEP home page (<http://ctep.cancer.gov>) or by calling the PMB at [contact]. The patient ID number (e.g., "44444") and the patient initials (e.g., "FL") should be entered in the "Lot Number" field. A separate line item is required for each patient ID number (e.g., "44444") that is being returned. Bottles with remaining tablets should be documented in the patient-specific NCI Investigational Agent Accountability Record (i.e., logged is as "returned by patient" and logged out as "destroyed on site") and destroyed on site in accordance with institutional policy.

**Drug Accountability:** The investigator, or a responsible party designated by the investigator, must maintain a careful record of the receipt, disposition, and return of all drugs received from the PMB using the NCI Investigational Agent Accountability Record for Oral Agents available on the CTEP home page (<http://ctep.cancer.gov>) or by calling the PMB at [contact]. A separate NCI Investigational Agent Accountability Record must be maintained for each patient ID number (e.g., "44444") on this protocol.

Rev. 10/16

**Emergency Unblinding**

The information provided below is for the use by a physician, nurse, CRA or pharmacist treating the patient. These contact numbers should not be used by patients. Patients should be instructed to call their doctor's office in the event of an emergency or adverse event that may result in the need to unblind the patient.

In the event of an emergency or severe adverse reaction necessitating identification of the medication for the welfare of the patient, please contact the Study Chair, [name], at [contact], or email: [[contact]](mailto:[contact]) first to ensure the reason for unblinding is valid. Then call a member of the ECOG-ACRIN Operations Office – Boston drug team at [contact] Monday through Friday between 9:00 AM and 5:00 PM Eastern Time. For unblinding outside of these hours, contact AnswerConnect at [name]. This service will request the reason for unblinding and then page the on-call ECOG-ACRIN staff who will return your call and provide the unblinded treatment assignment if applicable. Remember, AnswerConnect should only be contacted outside of normal business hours and only in the event of an emergency. The ECOG-ACRIN Operations Office – Boston or AnswerConnect will require the protocol number (i.e., "E2112"), the patient ID number (e.g., "44444"), and the patient initials (e.g., "FL") to unblind the patient. Note that if a patient is unblinded, he/she must discontinue protocol treatment.

NCI CTEP should also be notified of a request for unblinding

8.1 Entinostat/Placebo (NSC 706995) (IND# [REDACTED])

8.1.1 Other Names

MS-27-275, MS-275, SNDX-275

Rev. 10/16

Rev. 10/16	8.1.2	
Chemical Name
 
3-Pyridylmethyl N-{4-[(2-aminophenyl)carbamoyl]benzyl}carbamate

Rev. 10/16	8.1.3	
Classification
 
Histone deacetylase inhibitor (HDACi)

	8.1.4	
Molecular Formula
 
C21H20N4O3      M.W.: 376.41

Rev. 10/16	8.1.5	
Mode of Action
 
Histone deacetylases (HDACs) are a family of enzymes that regulate chromatin remodeling and gene transcription via the dynamic process of acetylation and deacetylation of core histones. Entinostat inhibits histone deacetylases, changes chromatin configuration, and induces differentiation and apoptosis of cancer cells through an epigenetic mechanism.

Rev. 10/16	8.1.6	
Storage and Stability
 
Store the bottles at controlled room temperature (15-25oC), and protect from light. Entinostat is not to be exposed to extremes of temperature (greater than 30°C or less than 5°C). Shelf life stability studies of the intact bottles are on-going.

	8.1.7	
Dose Specifics
 
Entinostat/Placebo 5mg once every week (days 1, 8, 15, and 22) of a 28 day cycle. See Section 5.4 for information regarding dose reductions. Entinostat/Placebo 1mg tablets are also available in case of dose reduction.

Rev. 10/16	8.1.8	
Route of Administration
 
Oral, on an empty stomach, at least 1 hour before and 2 hours after a meal. Entinostat tablets should not be split, crushed, or chewed.

Rev. 10/16	8.1.9	
Incompatibilities
 
Metabolism: Data from in vitro metabolism experiments in human tissues demonstrated that entinostat is not metabolized by CYP enzymes (Acharya 2006), but UGT 1A4 did metabolize entinostat to its M2 glucuronide metabolite. No metabolites could be detected after incubation of entinostat in human liver microsomes (Acharya 2006). While inhibition of CYP enzymes 2B6 and 3A4 was seen, the data show that the degree of the inhibition makes it unlikely that any in vivo systemic interactions would occur. Intestinal CYP 3A4 may be inhibited by entinostat. However, entinostat did not inhibit any UGT enzymes tested. Entinostat was found to induce CYP 1A2, CYP 2C6, and CYP 2B8 as well as UGT 1A4. Finally, entinostat was found to be a substrate for P-gp and BCRP transporters, but did not inhibit either of these transport proteins.

	8.1.10	
Availability
 
See Section 8.0 above for complete details.

Rev. 10/16

8.1.11 Side Effects  
See Section [5.3](#) for CAEPR.

8.1.12 Nursing/Patient Implications

Entinostat should be taken on an empty stomach, at least 1 hour before and 2 hours after a meal/snack. If the patient's dose requires more than one tablet, the tablets should be taken one at a time. Delay administration of H2-antagonists, antacids, or proton pump inhibitors, or other drugs that lower acidity for at least 2 hours after dosing entinostat.

Entinostat may cause fatigue or malaise; advise patient to exercise caution while driving a vehicle or operating machinery.

Administration of entinostat is contraindicated in patients with a history of allergy to entinostat or other medications that have a benzamide structure (eg, tiapride, remoxipride, clebropride).

Careful monitoring of patients for signs of infection or reactivation of past infections is recommended, as reactivation of infection has been reported in patients treated with entinostat, in some cases without evidence of neutropenia. The clinical significance of this finding and the potential association with entinostat is unknown.

Entinostat must not be used during pregnancy or while breast-feeding. Women and men participating in entinostat clinical studies must agree to use acceptable contraceptive methods, as indicated in the clinical study protocol, during treatment and for 3 months thereafter.

## 8.2 Exemestane

**NOTE:** Please refer to package insert for complete prescribing and toxicity information.

8.2.1 Other names

Aromasin

8.2.2 Chemical name

6-methylenandrosta-1,4-diene-3,17-dione

8.2.3 Classification

Exemestane is a steroidal aromatase inhibitor (inhibitor of estrogen synthesis).

8.2.4 Molecular Formula

C20H24O2

8.2.5 Mode of Action

Exemestane is an irreversible, steroidal aromatase inactivator, structurally related to the natural substrate androstenedione. It acts as a false substrate for the aromatase enzyme, and is processed to an intermediate that binds irreversibly to the active site of the enzyme causing its inactivation, an effect also known as "suicide inhibition". Exemestane significantly lowers circulating estrogen concentrations in

postmenopausal women, but has no detectable effect on adrenal biosynthesis of corticosteroids or aldosterone. Exemestane has no effect on other enzymes involved in the steroidogenic pathway up to a concentration at least 600 times higher than that inhibiting the aromatase enzyme. [Pfizer, Package Insert].

8.2.6 Storage and Stability

Store at 25°C (77°F); excursions permitted to 15°–30°C (59°–86°F). Exemestane tablets should remain in their original container.

8.2.7 Dose Specifics

Exemestane 25 mg once daily after a meal, days 1-28 of each cycle.

8.2.8 Route of Administration

Oral

8.2.9 Incompatibilities

CYP3A4 inducers: Caution, may significantly decrease exposure to exemestane. CYP 3A4 inhibitors: Significant pharmacokinetic interactions appear unlikely. [Pfizer, Package Insert]

8.2.10 Availability

Sites within the United States should refer to Section [8.0](#) above for complete details. Information for sites outside of the United States will be included once available.

8.2.11 Nursing/Patient Care Implications

Exemestane should be taken with food.

8.2.12 Adverse Effects

Advanced breast cancer: Most common adverse events were mild to moderate and included hot flushes (13% vs. 5%), nausea (9% vs. 5%), fatigue (8% vs. 10%), increased sweating (4% vs. 8%), and increased appetite (3% vs. 6%) for exemestane and megestrol acetate, respectively. [Pfizer, Package Insert] Please see the Exemestane Package Insert for more details on the known precautions, warnings, and adverse reactions.

8.3 Goserelin

**NOTE:** Please refer to package insert for complete prescribing and toxicity information. This will be used in pre/perimenopausal female and all male participants only in this clinical trial.

8.3.1 Other names

Zoladex

Rev. Add5  
Rev. Add7

- 
- 8.3.2 Chemical name  
Pyro-Glu-His-Trp-Ser-Tyr-D-Ser(But)-Leu-Arg-Pro-Azgly-NH2 acetate
- 8.3.3 Classification  
Goserelin is a GnRH agonist.
- 8.3.4 Molecular Formula  
C59H84N18O14
- 8.3.5 Mode of Action  
Goserelin is a synthetic decapeptide analogue of GnRH. It acts as an inhibitor of pituitary gonadotropin secretion when administered in the biodegradable formulation. In animal and *in vitro* studies, administration of goserelin resulted in the regression or inhibition of growth of the hormonally sensitive dimethylbenzanthracene (DMBA)-induced rat mammary tumor and Dunning R3327 prostate tumor. [AstraZeneca, Package Insert].
- 8.3.6 Storage and Stability  
Goserelin will be handled per routine pharmaceutical standards.
- 8.3.7 Dose Specifics  
Goserelin is available commercially as 3.6 mg doses in disposable syringe devices.
- 8.3.8 Preparation  
Not applicable, dose is ready for administration.
- 8.3.9 Route of Administration  
Subcutaneous injection
- 8.3.10 Availability  
Goserelin is commercially available and will be prescribed by the treating physician and covered by the patients insurance.
- 8.3.11 Adverse Effects  
Most common adverse events occurring in >10% of men: hot flashes, sexual dysfunction, decreased erections and lower urinary tract symptoms.
- 8.3.12 References  
AstraZeneca Package Insert  
[http://www1.astrazeneca-us.com/pi/zoladex3\\_6.pdf](http://www1.astrazeneca-us.com/pi/zoladex3_6.pdf)

Rev. Add5  
Rev. Add7

## 9. Statistical Considerations

### 9.1 Study Objectives

Rev.10/15

The primary objective of this randomized, placebo-controlled, double-blinded, phase III study is to determine whether Exemestane + Entinostat (Arm A) improves progression-free survival (PFS) and/or overall survival (OS) compared to the Exemestane + Placebo (Arm B) in patients with hormone receptor-positive, human epidermal growth factor receptor 2 (HER2)-negative locally advanced or metastatic breast cancer (MBC) who have experienced disease progression after non-steroidal AI use in the adjuvant setting (within 12 months prior to enrollment) or in the metastatic setting.

Both PFS and OS are primary endpoints, and the study is designed to show an improvement in either PFS or OS. PFS is defined to be time from randomization to the earliest of documented disease progression as defined by the Response Evaluation Criteria In Solid Tumors (RECIST) 1.1 criteria, new primary breast cancer, or death without progression. Disease assessment will continue until disease progression, even after non-protocol anti-cancer therapy is started. Cases with incomplete follow up or without adequate disease evaluations will be censored at the date last documented to be free of progression, regardless of whether non-protocol anti-cancer therapy is started or not. Tumor response and progression will be defined by central review, including time point-by-time point radiologist reader review at the ACR Imaging Core Lab for patients with radiographically measurable/evaluable disease, and/or an independent review committee for patients with measurable/non-measurable disease that is not radiographically evident (i.e., skin lesions). OS is defined to be time from randomization to death from any cause, censoring cases who had not died at the date last known alive.

This study is aimed to give adequate power for both PFS and OS comparisons. The one-sided type I error of 0.025 is split between two hypotheses tests to control the overall type I error rate for the whole trial. Specifically, type I error rate is 0.001 for PFS test and 0.024 for OS test.

Rev.10/15

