#### Interim analysis for OS tests

Regardless of PFS results, the first interim analysis of OS will be performed at the final PFS analysis time (expected to be 24 months after study activation-see Section [9.2.1](#)). Interim analysis for OS will then be performed biannually until either the criteria for early stopping (described below) are met or the total planned number of OS events has been reported. Of note, interim analyses will be skipped if the change in the information since the previous interim analysis is less than 10%. In addition, when the information time reaches 90% or more, interim analysis will not be conducted, and the final analysis of OS will be performed when full information is reached. These interim analyses will be monitored by ECOG-ACRIN DSMC. Table 9.2 shows the operating characteristics for OS endpoint.

At each interim analysis, the stratified log rank test statistic will be computed. To preserve the overall one-sided type I error rate at 2.4% for the OS endpoint, critical values for rejecting null hypothesis at the interim analyses will be determined using a truncated version of the Lan-DeMets spending function corresponding to the O'Brien-Fleming boundary (1979). If the boundary is crossed at an interim analysis or at the final analysis, then the null hypothesis will be rejected, and the Exemestane + Entinostat therapy is superior to the exemestane monotherapy in terms of OS. If the criteria for rejecting the null hypothesis are not met, then it will be concluded that this trial fails to show superiority of Exemestane + Entinostat therapy over the exemestane monotherapy on OS.

Because interim analyses are timed to coincide with the ECOG-ACRIN DSMC meetings, these boundaries may change depending on the number of observed OS events at that time. Also, because of

delays in data submission and processing, it is likely that actual analysis times will be 6-12 months later.

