**Table 9.2: Operating Characteristics for OS Endpoint**

Repeated Analysis	Real time (months)	Information time	Failures under alternative hypothesis	Nominal significance (one-sided)	Upper boundary
1	24	0.24	101	0.00048	3.3020
2	30	0.36	149	0.00048	3.3020
3	36	0.49	203	0.00068	3.2036
4	42	0.64	261	0.00400	2.6518
5	48	0.76	313	0.00805	2.4065
6	54	0.87	355	0.01193	2.2593
Final	64	1.00	410	0.01872	2.0808

If PFS test is negative in the primary analysis, this study will also be monitored for early stopping in favor of the null hypothesis (i.e., futility) for the OS test using the Jennison-Turnbull repeated confidence interval (RCI) method. At each interim OS analysis, the RCI on the observed hazard ratio will be computed using the critical values from the above error spending rate function. If the RCI does not include the alternative hazard ratio of 1.33 (arms B/A), then the OS comparison would be stopped early for lack of benefit. The observed hazard ratio will be calculated using stratified Cox proportional-hazards model, stratified on randomization stratification factors, without any other covariates. If the PFS test is positive in the primary analysis, no interim futility analysis for OS will be conducted.

As mentioned in Section 9.2.1, if the first interim analysis of OS is positive, the interim OS data will be released to Syndax and the public and the study will be stopped early for efficacy. If the first interim analysis of OS does not cross the efficacy boundary, then at the time study accrual is completed, if (1) the primary PFS test is positive at the 0.001 level, and (2) the estimated PFS hazard ratio for Exemestane + Entinostat vs. Exemestane + Placebo is  $< 0.675$ , the interim OS data will also be confidentially released to Syndax. The DSMC will also be asked to allow use of interim OS data from the first 360 patients enrolled in an application to the FDA, with the understanding that the data not be made public unless required as part of the FDA review process.

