The primary endpoints are progression-free survival (PFS) and overall survival (OS). Both of the two endpoints will be used for potential entinostat registration with FDA. ORR, toxicity and TTD are secondary endpoints. The primary analysis of PFS will include follow-up through the 247th PFS event within the first 360 patients enrolled. For the primary analysis, progression will be defined by central review. A sensitivity analysis for PFS will be performed using the first 360 patients based on progression defined by local investigators. The TTD analysis will include similar follow-up. The primary analyses of ORR and toxicity will include the first 360 patients enrolled. Final analysis for OS is expected to be conducted at about 70 months after study activation (40 months of accrual + 24 months of follow up + 6 months of data collection and cleaning). At the time of the final OS analysis, secondary analyses of the other endpoints (PFS, ORR and toxicity) including all cases enrolled will be conducted. The secondary analysis of PFS will be conducted in all 600 patients based on progression defined by the local investigators since central review is anticipated for the first 360 patients only.

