at diagnosis, prior adjuvant chemotherapy, prior hormonal therapy, et al. The assumption of proportionality in the Cox models will be assessed by investigating the weighted Schoenfeld residuals for each predictor. Patients with missing values for covariates will be excluded from modeling when the proportion of missingness is less than 5% and will be imputed appropriately if the proportion of missingness is  $\geq 5\%$ . ORR will be summarized along with the exact binomial 95% confidence interval and compared between the two arms using Fisher's exact tests.

TTD is defined as time from randomization to disease progression or death or worsening of symptoms, whichever occurs first. All primary analysis for TTD will be based on all cases receiving at least one dose of protocol treatment (i.e., all treated population). The distribution of TTD will be estimated using Kaplan-Meier method, and TTD comparisons between treatment arms will be tested primarily using log-rank test. Cox proportional-hazards models will be conducted to estimate the HR for treatment effect for TTD as a supportive analysis. Same factors included in the multivariable Cox model for PFS and baseline symptom level will be included as predictors for TTD.

Analyses pertaining to toxicity will be based on all treated cases. Adverse events will be graded using the National Cancer Institute (NCI) Common Terminology Criteria for Adverse Events (CTCAE). All treatment-emergent and baseline adverse events and hematological/biochemical toxicities based on laboratory measurements, as well as drug related AE's, will be summarized by treatment group and NCI CTCAE worst grade. The incidence of deaths and treatment-emergent serious adverse events (defined as number of patients experiencing the AE divided by all treated patients) will be summarized and compared between treatment arms using Fisher's exact test. Also, the incidence of adverse events leading to discontinuation of investigational product and/or withdrawal from the study will be summarized and listed.

In all analyses, P-values will be two-sided. A level of 0.2% will be considered statistically significant for stratified log rank test for the primary PFS analysis. For OS comparison, the significance level for stratified log rank test will be 4.8%. For all other tests, a level of 5% will be considered statistically significant.

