All above analyses for protein lysine acetylation change will be repeated for all three types of peripheral blood mononuclear cells (CD3+ T cells, CD19+ B cells and CD14+ monocytes). In all analyses, P-values will be two-sided and a level of 5% will be considered statistically significant. No adjustment will be made for multiple comparisons.

If PFS endpoint is positive in the primary analysis within the first 360 patients, the acetylation data will be analyzed for a subgroup analysis for PFS (all 360 patients will be dichotomized into one of two groups based on the whole sample median: > median and ≤ median) at the PFS primary analysis time.

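### Optional gain: the 0.001 (PFS) / 0.024 (OS) split is valid but passes no alpha to PFS once OS is rejected; one added rule would recover it

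*Combined protocol and SAP*

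**What the plan says.** Section 9.1 names PFS and OS as primary endpoints, counts an improvement in either one as success, and divides the one-sided 0.025: "Specifically, type I error rate is 0.001 for PFS test and 0.024 for OS test". The same section adds: "This study is aimed to give adequate power for both PFS and OS comparisons".

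Section 9.4 restates the split as fixed two-sided levels. For PFS: "A level of 0.2% will be considered statistically significant for stratified log rank test for the primary PFS analysis". OS has 4.8%. For everything else: "For all other tests, a level of 5% will be considered statistically significant". No second step follows a rejection of either hypothesis.

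The primary PFS data set is fixed: central review, first 360 patients, follow-up to the 247th PFS event (Sections 9.2.1 and 9.4). There is no interim efficacy test of PFS (Section 9.2). On timing, Section 9.2.3 says: "Regardless of PFS results, the first interim analysis of OS will be performed at the final PFS analysis time". A larger PFS analysis comes later and is labelled secondary: "The secondary analysis of PFS will be conducted in all 600 patients based on progression defined by the local investigators".

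Several rules depend on whether PFS is positive: the FDA submission on the first 360 patients (9.2), OS futility monitoring (9.2.3), the confidential release of interim OS data, which requires that "the primary PFS test is positive at the 0.001 level" and that the estimated PFS HR is below 0.675 (9.2.3), and the early acetylation analysis (9.5.2: "If PFS endpoint is positive in the primary analysis within the first 360 patients").

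**The concern.** With two primary hypotheses and a Bonferroni split, rejecting one frees its alpha for the other at no cost to family-wise error. The plan leaves this unused. Suppose OS is positive and the centrally reviewed PFS result has a one-sided p-value between 0.001 and 0.025. PFS, a primary endpoint, then still cannot carry an error-controlled claim, although a closed test of the same two hypotheses would allow one.

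What is at stake is limited: a formal PFS conclusion beside an OS conclusion already won. Whether the trial succeeds under its own either-endpoint definition is not affected.

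**Working it through.** **1. The plan's own figures.** With d events, 1:1 allocation and hazard ratio HR, the log-rank statistic has mean |ln HR| x sqrt(d)/2.
- PFS (247 events, HR 0.58, one-sided 0.001): 0.5447 x 15.716/2 = 4.280; 4.280 - 3.090 = 1.190; power 88.3%. The plan states 88.5%.
- OS (410 events, HR 0.75): simulating the seven Table 9.2 boundaries gives one-sided type I error 0.0240 and power 81.2%. The plan states 80%.
- Total alpha: 0.001 + 0.024 = 0.025.

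**2. Where the two PFS thresholds fall.** The critical HR is exp(-2z/sqrt(247)). Months gained use the 4.1-month control median and exponential PFS, as in Section 9.2.1.
- One-sided 0.001: exp(-2 x 3.0902/15.716) = 0.675; 4.1/0.675 - 4.1 = 2.0 months.
- One-sided 0.025: exp(-2 x 1.9600/15.716) = 0.779; 4.1/0.779 - 4.1 = 1.2 months.

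The step therefore concerns observed PFS HRs from about 0.675 to 0.779.

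**3. Validity.** The rule is: claim PFS if p < 0.001, or if OS crosses its boundary and p < 0.025.
- Both nulls true: a false claim requires p < 0.001 for PFS or an OS crossing, so the error is at most 0.001 + 0.024 = 0.025.
- Only the PFS null true: every PFS claim has p < 0.025, so the error is at most 0.025.
- Only the OS null true: the OS boundary is unchanged, so the error is at most 0.024.

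No look is added, because the same frozen PFS p-value meets a second threshold.

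**4. Hand check of the gain.** PFS power at 0.025 is 99.0% (4.280 - 1.960 = 2.320). With independent statistics and no early stops, the chance of a PFS claim is 0.883 + 0.812 x (0.990 - 0.883) = 0.970.

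**5. Simulation.** This includes the PFS stops (HR above 1.52, 0.981 and 0.941 at 25%, 35% and 65% information), the Table 9.2 boundaries, and the OS futility rule when PFS misses 0.001. Ranges cover an assumed correlation of 0 to 0.6 between the final PFS and OS statistics.

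| PFS HR | OS HR | PFS claim, now | PFS claim, with step | Both claimed, now | Both claimed, with step |
|---|---|---|---|---|---|
| 0.58 | 0.75 | 88% | 93-96% | 72-76% | 80-81% |
| 0.65 | 0.75 | 61% | 82-85% | 50-57% | 74-77% |
| 0.73 | 0.75 | 27% | 60-62% | 22-26% | 55-61% |
| 0.58 | 0.85 | 88% | 89-92% | | |
| 0.65 | 0.85 | 61% | 66-72% | | |
| 0.73 | 0.85 | 27% | 41% | | |

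PFS HR 0.73 is the phase 2 value in Table 1.1. At OS HR 1.0 the gain is 1 point or less. In the first row, the PFS claim with the step is 96.5%, 95.0% and 93.0% at correlation 0, 0.3 and 0.6. The chance of at least one positive endpoint is 97.1%, 95.4% and 93.2% under both rules.

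**6. Error on PFS alone.** With PFS null and OS HR 0.75, false PFS claims go from 0.001 to 0.019-0.024.

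**7. The all-600 PFS analysis.** Uniform accrual over 40 months and exponential PFS give about 592-596 events at month 64. The 5% two-sided level is met at HR up to exp(-2 x 1.96/sqrt(592)) = 0.85. Assume the same true HR under central and local review, and 247 events nested in 590. This test is then significant while the primary PFS test misses in about 12%, 38% and 70% of trials at PFS HR 0.58, 0.65 and 0.73. With the step and OS HR 0.75 the figures are about 3-7%, 13-18% and 33-38%.

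**The case against.** The strongest reply is that nothing is broken. Success is defined as either endpoint, and OS power, the chance of at least one positive endpoint and the submission trigger would all stay the same. The stated aim of adequate power for both comparisons is already met marginally, at 88.5% and 80%, and the plan sets no target for winning both. The strict PFS bar also looks deliberate: 0.675, the HR required for release of interim OS data, equals the critical HR at 0.001. All of this stands, which is why the point is optional.

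It is also fair that the gain comes with a weaker PFS standard. The error on PFS alone rises roughly twenty-fold when OS works, and an effect of about 1.2 months becomes claimable against a 3.0-month design target. The family-wise bound is still kept.

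The documents do not support three stronger readings. A reader might infer that the split fails to control error or leaves PFS underpowered; steps 1 and 3 show neither. A reader might see the all-600 analysis at 5% as a second route to a PFS claim, but Sections 9.2 and 9.4 call it secondary and give the primary PFS test its own level. A reader might also expect the step to remove nearly all disagreement between the two PFS analyses. It does not, because the retest happens only when OS is rejected.

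Reference 47 in the list concerns recycling in Bonferroni-based tests, but the text available neither cites it nor states such a rule. Nothing about intent follows.

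**Conclusion.** The concern holds as an optional improvement, not as an error. Passing the OS alpha to PFS after an OS rejection adds about 5 to 8 percentage points to the chance of a formal PFS claim at the design effects, and similarly to the chance of claiming both endpoints. It costs no patients and no OS power.

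The mechanism and the error bound are certain. The size rests on the PFS-OS correlation, which is assumed. Over the wider range 0 to 0.8, without PFS stops, the chance of a PFS claim is 91-97% against 88%. The benefit needs OS to succeed: at PFS HR 0.58 it falls to about 1-4 points at OS HR 0.85 and to almost nothing at OS HR 1.0. It is larger if the true PFS effect is weaker than designed while OS holds.

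**What to change.** Add one rule to Sections 9.1 and 9.4: if OS is rejected at any OS analysis at its 0.024 group-sequential boundary, the primary PFS hypothesis is also tested at one-sided 0.025 (two-sided 5%), using only the frozen data set (central review, first 360 patients, through the 247th PFS event).

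State with it:
- The FDA submission, data release, HR below 0.675, OS futility and early acetylation rules all stay on the 0.001 test. This needs clarifying sentences in Sections 9.2, 9.2.1, 9.2.3 and 9.5.2.
- A PFS result released near month 40 that misses 0.001 is reported as not significant at that level, with a retest only if OS is later rejected.
- The rule is adopted before the primary PFS analysis by people blinded to interim PFS and OS results. Under Sections 9.2.1 and 9.9 the study statistician and the DSMC hold those results, so once results exist they cannot be the ones to adopt it. The documents do not show whether that analysis has already taken place. If it has, or if blinded adoption is not possible, leave the split as written.

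The cost is a few sentences, with no added look and no change to Table 9.2. The drawbacks to accept are the higher PFS-specific error (bounded by 0.025), the smaller claimable effect, and a PFS conclusion that may change between about month 40 and month 70.
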